8.2.2 RELATIONSHIP TO STUDY AGENT

The site principal investigator is responsible for designating, at the time an AE is reported, how likely it is that the AE is caused by the study intervention. This determination requires clinical judgement, but for purposes of this study an algorithm is used to help the investigator provide reporting that is as objective as possible and consistent with reporting across the trial.

Modified for EROCA, based upon: Adverse Events Reporting Requirements SOP. NIH-NIAID. <http://www.niaid.nih.gov/ncn/sop/adverseevents.htm> , accessed 11-30-04.

Not related: The temporal relationship between treatment exposure and the adverse event is unreasonable or incompatible and/or adverse event is clearly due to extraneous causes (e.g., underlying disease, environment)

Unlikely: May have reasonable or only tenuous temporal relationship to intervention. Must meet both of the following conditions:

- Could readily have been produced by the subject's clinical state, or environmental or other interventions.
- Does not follow known pattern of response to intervention.

Possibly: Must meet any 2 of the 3 following conditions

- Has a reasonable temporal relationship to intervention.
- Could not readily have been produced by the subject's clinical state or environmental or other interventions.
- Follows a known pattern of response to intervention.

Probably: Must meet all 3 of the following conditions

- Has a reasonable temporal relationship to intervention.
- Could not *readily* have been produced by the subject's clinical state or have been due to environmental or other interventions.
- Follows a known pattern of response to intervention.

Definitely: Must meet all 3 of the following conditions

- Has a reasonable temporal relationship to intervention.
- Could not *possibly* have been produced by the subject's clinical state or have been due to environmental or other interventions.
- Follows a known pattern of response to intervention.

8.2.3 EXPECTEDNESS

The site principal investigator will be responsible for determining whether an AE is expected or unexpected. An AE will be considered unexpected if the nature, severity, or frequency of the event is not consistent with the risk information previously described for the study agent.

8.3 TIME PERIOD AND FREQUENCY FOR EVENT ASSESSMENT AND FOLLOW-UP

The occurrence of an AE or SAE may come to the attention of study personnel during study visits and interviews of a study participant presenting for medical care, or upon review by a study monitor. All AEs including local and systemic reactions not meeting the criteria for SAEs will be captured on the appropriate RF. Information to be collected includes event description, time of onset, clinician's assessment of severity, relationship to study product (assessed only by those with the training and authority to make a diagnosis), and time of resolution/stabilization of the event. All AEs occurring while on study must be documented appropriately regardless of relationship. All AEs will be followed to adequate resolution.

Any medical condition that is present at the time that the participant is screened will be considered as baseline and not reported as an AE. However, if the study participant's condition deteriorates at any time during the study, it will be recorded as an AE. UPs will be recorded in the data collection system throughout the study.

Changes in the severity of an AE will be documented to allow an assessment of the duration of the event at each level of severity to be performed. AEs characterized as intermittent require documentation of onset and duration of each episode.

The PI or designated research staff will record all reportable events with start dates occurring any time after study enrollment until 24 hours (for non-serious AEs) or 90 days or last day of study participation (for SAE's). At each study visit, the investigator or study coordinator will inquire about the occurrence of SAEs since the last visit. Events will be followed for outcome information until resolution or stabilization.

8.4 REPORTING PROCEDURES

An adverse event (AE) is any unfavorable and unintended sign (including a clinically significant abnormal laboratory finding), symptom, or disease temporally associated with the use of a medical treatment or procedure regardless of whether it is considered related to the medical treatment or procedure (attribution of unrelated, unlikely, possible, probable, or definite). Each AE is a unique representation of a specific event used for medical documentation and scientific analysis.

A serious adverse event (SAE) is an AE that is fatal or life threatening, is permanently or substantially disabling, requires or prolongs hospitalization, results in a congenital anomaly, requires intervention to prevent permanent impairment or damage, or any event that the treating clinician or internal medical monitor judges to be a significant hazard, contraindication, side effect, or precaution. Reporting serious adverse events (SAEs) are based on the guidelines of the International Conference on Harmonization (ICH).

8.4.1 ADVERSE EVENT REPORTING

All AEs occurring within 24 hours of study participation and all serious adverse events (SAEs) occurring up until 90 days or last day of study participation are recorded on the online AE case report form (CRF) through the study database. The Site PI or Study Coordinator or designee is responsible for entering any and all AEs and SAEs into the database as soon as he/she becomes aware of the event and updating the information (e.g., date of resolution, action taken) in a timely manner. All non-serious AEs must be recorded on the electronic AE CRF within 5 days from the time it was discovered by the site study personnel. (All non-serious AEs during hospitalization must be entered within 5 days of discharge or end of study for that subject.) For SAEs, the data entry must take place within 24 hours of discovery of the event.

The Site PI is responsible for the monitoring and follow-up of AEs until resolution (or end of study for that subject) and appropriate documentation in the subject research record. In addition to performing protocol-specified follow up, the participating PI must review all previously reported ongoing AEs to evaluate the current status. If an AE that was previously reported on the Adverse Event CRF fully resolves and then recurs at a later date, the second occurrence is considered a new AE and a new Adverse Event CRF must be completed. Likewise, if an SAE that was previously reported and subsequently fully resolved later recurs at a level requiring expedited reporting, the SAE must be reported as a new SAE on the Adverse Event CRF.

Upon completion of the study protocol by the subject, premature withdrawal from the study by the subject, or subject's death, all information regarding each AE must be completed, if not done so earlier.

8.4.2 SERIOUS ADVERSE EVENT REPORTING

The study clinician will complete a SAE Form within the following timelines:

All Serious Adverse Events (SAEs) occurring during a subject's study participation will be recorded up until 90 days or last day of study participation. All SAEs must be entered into the database system within 24 hours of first

knowledge of the SAE. Additionally, all current study data for that particular subject must be entered to allow for timely review.

The study investigator shall complete an Unanticipated Adverse Device Effect Form and submit to the study sponsor and to the reviewing IRB as soon as possible, but in no event later than 10 working days after the investigator first learns of the effect. The study sponsor contact information is provided in Section 1, Key Roles. The study sponsor is responsible for conducting an evaluation of an unanticipated adverse device effect and shall report the results of such evaluation to FDA and to all reviewing IRBs and participating investigators within 10 working days after the sponsor first receives notice of the effect. Thereafter the sponsor shall submit such additional reports concerning the effect as FDA requests.

8.4.3 UNANTICIPATED PROBLEM REPORTING

Incidents or events that meet the OHRP criteria for UPs require the creation and completion of an UP report form. It is the site investigator's responsibility to report UPs to their IRB and to the DCC/study sponsor. The UP report will include the following information:

- Protocol identifying information: protocol title and number, PI's name, and the IRB project number;
- A detailed description of the event, incident, experience, or outcome;
- An explanation of the basis for determining that the event, incident, experience, or outcome represents an UP;
- A description of any changes to the protocol or other corrective actions that have been taken or are proposed in response to the UP.

To satisfy the requirement for prompt reporting, UPs will be reported using the following timeline:

UPs that are SAEs will be reported to the IRB and to the DCC/study sponsor within 7 days of the investigator becoming aware of the event.

Any other UP will be reported to the IRB and to the DCC/study sponsor within 7 days of the investigator becoming aware of the problem.

All UPs should be reported to appropriate institutional officials (as required by an institution's written reporting procedures), the supporting agency head (or designee), and OHRP within 7 days of the IR's receipt of the report of the problem from the investigator.

An investigator shall submit to the sponsor and to the reviewing IRB a report of any unanticipated adverse device effect occurring during an investigation as soon as possible, but in no event later than 10 working days after the investigator first learns of the effect (21 CFR 812.150(a)(1)), A sponsor who conducts an evaluation of an unanticipated adverse device

effect under 812.46(b) shall report the results of such evaluation to FDA and to all reviewing IRB's and participating investigators within 10 working days after the sponsor first receives notice of the effect. Thereafter the sponsor shall submit such additional reports concerning the effect as FDA requests (21 CFR 812.150(b)(1)).

8.4.4 EVENTS OF SPECIAL INTEREST

Not applicable

8.4.5 REPORTING OF PREGNANCY

Patients who are obviously pregnant will not be enrolled. If pregnancy is discovered, the team will request permission to follow pregnant women to pregnancy outcome. As the intervention (early transport with mechanical CPR) occurs prior to laboratory testing, no additional treatment is possible under this protocol after the discovery of pregnancy and patients are only on the protocol for the collection of outcomes.

8.5 STUDY HALTING RULES

No formal quantitative stopping rules are in place for EROCA. The study may be modified or discontinued at any time by the IRB, the NHLBI, the sponsor, the OHRP, the FDA, or other government agencies as part of their duties to ensure that research subjects are protected.

8.6 SAFETY OVERSIGHT

Safety oversight will be under the direction of an independent DSMB composed of individuals with the appropriate expertise, including emergency medicine. The DSMB will meet at least semiannually to assess safety and efficacy data on each arm of the study. The DSMB will operate under the rules of an approved charter that will be written and reviewed at the organizational meeting of the DSMB. At this time, each data element that the DSMB needs to assess will be clearly defined. The DSMB will provide its input to NIH. We will provide tables providing all SAEs by group, along with clinical outcomes, and a listing of SAEs by individual enrolled (given the small sample size of EROCA), as part of reporting to DSMB.

9 CLINICAL MONITORING

Clinical site monitoring is conducted to ensure that the rights and well-being of human subjects are protected, that the reported trial data are accurate, complete, and verifiable, and that the conduct of the trial is in compliance with the currently approved protocol/amendment(s), with GCP, and with applicable regulatory requirement(s).

- Designated study staff not involved with the enrollment will conduct monitoring. This will occur throughout the study, and will involve targeted or review of certain data (primary

endpoints, safety endpoints, consent forms). Monitoring reports will be distributed to the PI or site PIs if applicable.

- Independent audits will not be conducted.
- Each clinical site will perform internal quality management of study conduct, data collection, documentation and completion. As necessary, individualized quality management plans will be developed to describe a site's quality management.

10 STATISTICAL CONSIDERATIONS

10.1 STATISTICAL AND ANALYTICAL PLANS

This is a pilot trial, designed to demonstrate proof of feasibility prior to a larger scale trial that will be powered to improve patient outcomes. The primary endpoints target process measures, namely the delivery of randomized patients to the qualified ED within 30 minutes of qualifying event.

10.2 STATISTICAL HYPOTHESES

- Co-Primary Endpoint(s): Arrival to qualified ED within 30 minutes

We hypothesize that the proportion of patients randomized to early transport arriving at the hospital within 30 minutes will be greater than the historical proportion of 38.7%.

- Co-Primary Endpoint(s): Initiation of ECPR within 30 minutes of ED arrival

We hypothesize that greater than or equal to 80% of patients will have ECPR (qualifying ED standard care process) initiated within 30 minutes of ED arrival.

10.3 ANALYSIS DATASETS

The analytic datasets will use a modified per-protocol population. Patients who are assigned to early transport and do not have ROSC after initial rhythm analysis (and shock if indicated) and have the early transport initiated will be considered the primary analytic population for the ED arrival endpoint. Patients who are randomized to early transport and remain in cardiac arrest for at least 10 minutes after ED arrival and have the institutional standard care ECPR process initiated are considered the primary analytic population for the ECPR initiation endpoint. Exploratory clinical and safety endpoints will be collected on the entire population of refractory OHCA patients enrolled/randomized to either early transport or usual care.

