5.2 PARTICIPANT EXCLUSION CRITERIA

Exclusion criteria include:

- Sustained return of spontaneous circulation (ROSC)
- DNAR or DNI advanced directive
- Preexisting evidence of opting out of study
- Prisoner
- Pregnant (obvious or known)
- ECPR capable ED is not at the destination hospital as determined by EMS
- LAR/Family member aware of study and refuses study participation at the scene

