5.3 STRATEGIES FOR RECRUITMENT AND RETENTION

There is no participant “recruitment” for this study as it is not possible to prospectively identify victims of out-of-hospital sudden cardiac arrest and obtain informed consent. Participants will be included in the study if they meet enrollment criteria at the time of their cardiac arrest. Based on historical data, we anticipate randomizing 30 refractory OHCA patients over 18 months. This clinical trial will be conducted under exception from informed consent (further details in Section 13).

Patients will be screened and assigned a randomization group at the time of dispatch. Study eligibility and randomization will be further determined with the aid of an algorithm or expected time to eligible hospital map where a 911 dispatch operator will input eligibility data points and receive one of 3 responses. This is pre-enrollment treatment group assignment. Despite assignment to one of these three groups, the patient will not be considered randomized until they have met the inclusion criteria (including the refractory nature of the cardiac arrest.)

1. Not eligible continue usual resuscitative care (stay in place until ROSC or resuscitation

meets termination criteria)

2. Eligible, randomized to usual care (operationally same as 1 for paramedics)
3. Eligible, randomized to early transport

After an initial rhythm assessment and shock delivery (if indicated), patients who do not have ROSC will be considered randomized. Based on the assignment given at the time the prehospital providers were dispatched, they will either continue usual care (stay in place until ROSC) if assigned to that group (control), or undergo expedited transport with mechanical CPR device in place (experimental group). Patients who do not meet inclusion criteria or have exclusion criteria will not be considered randomized or enrolled, since no experimental procedures will occur to them (standard procedure is for patients to be transported after ROSC). If ROSC is achieved during transport or in the emergency department (experimental group), they will be included in the primary analysis of the expedited transport group. All patients will be followed for clinical outcomes.

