7.3.2 ENROLLMENT/BASELINE

Pre-hospital run sheet(s) will be reviewed for study eligibility and enrollment criteria. The emergency department and hospital electronic medical record will be reviewed for continued inclusion criteria, including time intervals from 911 call to randomization and 911 call to

emergency department admission, if applicable. Until hospital discharge, all data collected will come from previously collected medical records.

Initial Enrollment/Field Baseline (Day 0)

Patients will be enrolled and randomized if they meet the inclusion criteria, namely, the presence of refractory cardiac arrest (defined as no ROSC after initial rhythm analysis and shock if indicated). The treatment group was pre-assigned during the screening phase, but patients with immediate ROSC are considered screened out of the study as no experimental intervention will occur to them.

Patients with persistent cardiac arrest in the field who are randomized will be followed for clinical outcomes per the protocol whether or not they have ECPR.

Due to the sudden and urgent nature of cardiac arrest, treatment must occur immediately. Enrollment will occur at the time of randomization by the prehospital providers at the scene of the out-of-hospital cardiac arrest. Patients will be enrolled under the exception from informed consent (EFIC) process.

Prehospital Medical Records

Prehospital run reports is where Basic Life Support (BLS) and Advanced Life Support (ALS) document the events of the 911 call and often become part of the medical record when patients are brought to the emergency department. Any run reports not found in the medical record and for participants who dies prior to the emergency department will be collected directly from the agencies.

EMS medical records will be reviewed and the following data abstracted:

- Date and time of 911 call
- Time of index cardiac arrest
- Status of witnessed arrest
- Status of Bystander CPR
- Time of collapse
- Time CPR initiated
- Duration of EMS CPR
- Initial recorded cardiac arrest rhythm
- Use of Impedance-threshold device
- Use and type of advanced airway
- Location of cardiac arrest (home, public place, parking lot, street, etc.)
- Date and time of ED arrival

Index Cardiac Arrest/Emergency Department (Day 0)

Emergency Department (ED) medical records will be reviewed and the following data abstracted:

- Date and time of ED arrival
- Status and timing of ROSC
- Demographic information
- Physician progress note(s)

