10.4.2 ANALYSIS OF THE PRIMARY EFFICACY ENDPOINT(S)

Co-Primary Endpoint(s): Arrival to qualified ED within 30 minutes

The proportion of qualifying episodes to arrive at the ED within 30 minutes will be compared to our historical data point estimate of 38.7% using a one sample exact test of binomial proportions at the 0.05 two-sided significance level.

Co-Primary Endpoint(s): Initiation of ECPR within 30 minutes of ED arrival

Using the modified intention to treat population with ongoing cardiac arrest in the qualified ED, we will declare the analysis of this objective successful if 80% or more of patients have ECPR (qualifying ED standard care process) initiated within 30 minutes of ED arrival. No formal hypothesis test will be conducted.

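### The ED-arrival test is restricted to early-transport patients in whom transport was started, while the hypothesis covers everyone randomized to early transport, and no all-randomized proportion is planned

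*Combined protocol and SAP*

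**What the plan says.** All references are to the combined protocol and SAP.

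- **10.1** describes the process target as "namely the delivery of randomized patients to the qualified ED within 30 minutes of qualifying event".
- **10.2** states the hypothesis for "the proportion of patients randomized to early transport arriving at the hospital within 30 minutes", to exceed the historical 38.7%.
- **10.3** calls its datasets modified per-protocol. For ED arrival it takes patients assigned to early transport with no ROSC after the initial rhythm analysis (and any indicated shock) "and have the early transport initiated will be considered the primary analytic population for the ED arrival endpoint".
- **10.4.2**, which holds the test, reads: "The proportion of qualifying episodes to arrive at the ED within 30 minutes will be compared to our historical data point estimate of 38.7" percent. It uses a one-sample exact binomial test at two-sided 0.05. The second co-primary, ECPR initiation, is an 80% threshold with no test.
- **5.3** fixes the moment of randomization. After the initial rhythm assessment and any shock, "patients who do not have ROSC will be considered randomized". **7.3.2** agrees: "Patients will be enrolled and randomized if they meet the inclusion criteria, namely, the presence of refractory cardiac arrest". Both points come before transport.
- **10.4.5** plans a qualitative summary of why assigned pathways were not followed. **10.4.10** plans a table of individual primary-endpoint data without naming its population.
- On later ROSC, **5.3** says: "If ROSC is achieved during transport or in the emergency department (experimental group), they will be included in the primary analysis". **10.4.1** is wider and includes any test-arm patient whose ROSC comes before ECPR is started.

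**The concern.** One endpoint has three descriptions of its denominator, and at least two of them differ in substance. A patient randomized to early transport but never moved is inside 10.2 and outside 10.3. The plan foresees such patients, since 10.4.5 will describe why pathways were not followed, but no section plans an ED-arrival proportion that includes them.

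Section 3 gives the purpose of this co-primary as establishing that the early transport protocol is feasible. Starting transport is the first step of that protocol, so failing to start is itself a feasibility failure. Section 10.3 removes that failure from the only tested endpoint. The trial is open-label and the initiation condition is met or missed after randomization, so the denominator should be settled before results are seen.

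ROSC on scene after randomization but before departure adds a smaller gap. Read literally, 10.4.1 includes such a patient in the primary analysis. Section 10.3 includes the patient only if early transport was initiated, and does not say whether a move after ROSC would count.

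**Working it through.** **Inputs.** Null proportion p0 = 0.387 and exact two-sided test at 0.05 (10.4.2). n = 24 and on-time rate 19/24 = 79.2% (10.5). The number never moved, d, is not in the documents. I assume d = 1 to 4 out of 24 randomized to early transport, with never-moved patients not arriving in time.

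**1. The plan's own power.** With n = 24, P(X ≥ 14 | 0.387) = 0.040 and P(X ≥ 15 | 0.387) = 0.0156, so the upper rejection region at 0.025 is X ≥ 15. Power = P(X ≥ 15 | 24, 19/24) = 98.3%. This reproduces the 98% in 10.5, which is not in dispute.

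**2. The denominators side by side.**

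| Section | Denominator | Never-moved patient |
|---|---|---|
| 10.1 | randomized patients | in |
| 10.2 | randomized to early transport | in |
| 10.3 | as 10.2, and transport initiated | out |
| 10.4.2 | qualifying episodes, not tied to 10.3 | unclear |

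**3. Shift in the proportion.** Expected all-randomized proportion = (19/24) × (24 − d)/24. Each never-moved patient costs 79.2/24 = 3.3 points.

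| d | 10.3 set | All randomized |
|---|---|---|
| 0 | 79.2% | 79.2% |
| 1 | 79.2% | 75.9% |
| 2 | 79.2% | 72.6% |
| 3 | 79.2% | 69.3% |
| 4 | 79.2% | 66.0% |

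**4. Chance that the test result differs.** The on-time count is S ~ Binomial(24 − d, 19/24). The all-randomized test rejects upward from 15 of 24. The results differ when S is 14 or less but still rejects with denominator 24 − d. Section 10.4.2 does not say which two-sided exact p-value is meant, so both common versions are shown.

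| d | Minimum-likelihood: counts, chance | Equal-tail: counts, chance |
|---|---|---|
| 1 | 14, 2.3% | none, 0% |
| 2 | 14, 4.3% | 14, 4.3% |
| 3 | 13 and 14, 11.0% | 14 only, 7.5% |
| 4 | 13 and 14, 18.4% | 13 and 14, 18.4% |

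The versions part at 14/23 (p = 0.033 minimum-likelihood, 0.052 equal-tail) and at 13/21 (0.041 and 0.053). The equal-tail version is the one that corresponds to Clopper-Pearson intervals.

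**5. One illustration, d = 4 and S = 14.**
- 10.3 set: 14/20 = 70.0%, exact 95% CI 45.7 to 88.1, minimum-likelihood p = 0.005.
- All randomized: 14/24 = 58.3%, CI 36.6 to 77.9, p = 0.059.
- With one more on time, 15/24 rejects again (p = 0.021).

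**6. Power for the all-randomized set.** With n = 24, power = P(X ≥ 15) at success rate (19/24) × initiation share.

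| Initiation share | Success rate | Power |
|---|---|---|
| 100% | 79.2% | 98.3% |
| 95% | 75.2% | 94.8% |
| 90% | 71.3% | 87.8% |
| 80% | 63.3% | 62.3% |

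**The case against.** Section 10.3 is where analysis sets are defined. It names its set openly as per-protocol and defines the denominator in one sentence. The wording of 10.4.2 can be read as shorthand for that set. Arrival among patients actually transported is a legitimate target in a pilot. The test is single-arm against a historical value, and 10.4.1 says randomization is not meant to produce comparable groups, so no between-arm comparison is biased. Non-initiation is not concealed either: reasons are summarised, individual data are tabulated, and 5.3 and 7.3.2 follow all randomized patients for clinical outcomes.

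Most of this stands. It rules out reading 10.3 as a hidden or improper exclusion. It does not make the 10.3 proportion the one hypothesised in 10.2. An all-randomized figure could be rebuilt from the 10.4.10 table only if never-moved patients are listed there, which is not stated.

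A reader might also infer that the ROSC rules conflict throughout the protocol, because the ROSC exclusion in 5.2 carries no time point. That goes too far. Sections 5.3, 7.3.2 and 10.3 all place the ROSC screen at the initial rhythm analysis and shock. What remains is mainly 10.4.1 against the initiation condition in 10.3.

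**Conclusion.** The inconsistency is clear on the text and should be fixed. As written, 10.3 estimates on-time arrival among patients whose transport was started, and this overstates the 10.2 quantity whenever never-moved patients do not arrive in time. Under the stated assumptions (24 randomized, 79.2% on time among those moved), the overstatement is about 3.3 points per never-moved patient and zero if all are moved. The non-initiation rate is unknown, so confidence attaches to the mismatch and not to any one figure.

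A reader might infer that the significance test is likely to be overturned. The calculations do not support that: the chance of a different result is 0 to 2.3% with one never moved, 4.3% with two, 7.5 to 11.0% with three and 18.4% with four. Nor can a missed success criterion be claimed. Section 10.5 writes it as a count out of 24 and does not say how it applies to a smaller set.

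**What to change.** 1. Pre-specify the on-time proportion among all patients randomized to early transport. Count anyone not at the qualified ED within 30 minutes as not meeting the endpoint. Use the same exact test, with an exact 95% CI.
2. Make this the analysis of the 10.2 hypothesis. At minimum, report it beside the 10.3 per-protocol result and reword 10.2 and 10.4.2 to name the 10.3 set.
3. Reconcile 10.4.1 with the initiation condition in 10.3, so that the analysis sets state one counting rule for ROSC on scene after randomization and before transport.

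**Cost.** Wording changes and one extra proportion. No new data are needed, because 7.3.2 already abstracts the times of the 911 call, index arrest and ED arrival.

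**Downside.** The estimate will be less favourable if some patients are never moved, and power for the all-randomized set falls to 94.8%, 87.8% or 62.3% at 95%, 90% or 80% initiation. The documents do not say which 2014 patients underlie the 38.7%. If that figure covers only transported patients, comparing the all-randomized proportion with it would be conservative, and the report should say so.
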